4.2. Exclusion criteria

No group will be excluded from this study.

4.3. Recruitment

The study sample will include retrospectively all patients who have undergone PGTM, matching the inclusion and exclusion criteria cited above. Data of children included in the study are retrieved from the database of Reproductive Medicine Unit (Fertility Center) in which their mothers information about the IVF cycle and results of PTGM are recorded.

5. STUDY ASSESSMENT

The study is not associated with any adverse effects or risks.

6. STATISTICAL CONSIDERATIONS

6.1. Sample size

For the purpose of the study all the children born from single thawed embryos in Fertility Center from the beginning to 2016, will be included in the study, and the sample is 567.

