
Study Objectives
	
The primary objective of this retrospective observational single-center study is to describe the efficacy of PGT-M in a real-life setting. Efficacy will be evaluated in terms of live birth rate (LBR), simple and cumulative live birth rate (CLBR) per couple, and abortion rate (AR). Furthermore, investigators will consider how many cycles the participants need to undergo to achieve a viable blastocyst.
 
The secondary objective is to evaluate the incidence of aneuploidy in tested embryos, in order to understand the need for PGTA in addition to PGTM.

Study Endpoints/Outcomes
	
For the evaluation of the study objectives, all patients that underwent PGTM from 2016 to 2022 will be included in the study.
 
The results obtained from the PGT-M will be calculated as:
 
Live birth rate (LBR): defined as the “the number of deliveries that resulted in at least one live birth, divided by the number of cycles.” Embryology and Alpha Scientists in Reproductive Medicine. Electronic address [1]
 
Cumulative live birth (CLBR) per couple: defined as the “delivery of at least one live-born infant (>24 weeks of gestation) in the fresh or in the subsequent frozen-thawed cycles in relation to the number of oocytes retrieved per couple.” Polyzos, Drakopoulos [2]
 
Abortion rate (AR): is defined as the “spontaneous demise of a pregnancy before the foetus reaches viability. The term therefore includes all pregnancy losses (PLs) from the time of conception until 24 weeks of gestation.” Group, Vlaisavljevic [3]
 
Aneuploid embryo rate: “the most common genetic abnormality

	resulting in embryonic demise, pregnancy loss, and congenital birth defects. At the preimplantation stage, ~50% of the IVF-derived embryos have chromosomal abnormalities that are incompatible with implantation or normal fetal development.” Hindi E. Stohl [4]
Study design	Monocentric retrospective observational study
Product/Intervention	PGT-M is an option for all patients, fertile and infertile, who are at risk of transmitting a monogenic disease to their offspring. PGT-A is only performed on unaffected embryos that have undergone PGT-M; therefore, investigators do not know the percentage of aneuploidy in affected embryos.
Eligibility Criteria	Patients fertile or infertile that have undergone preimplantation genetic testing for monogenic diseases (PGTM). No exclusion criteria will be considered.

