Study Procedures	The information collected for the database will be retrieved from the Fertility Center internal web-based registry where data about pregnancy follow up are noted. The study database includes all PGTM cycles performed between 2016-2022 at the Humanitas Fertility Center.
Number of patients (planned)	All 76 patients who underwent PGTM testing in the Fertility Center starting from the beginning of 2016 and going through the end of 2022 will be included in the study.
Investigational Sites (planned)	University affiliated 3 rd level Fertility Center
Sample size and statistical consideration	Data will be described as number and percentage, if categorical, or mean and standard deviation, if continuous and approximately Gaussian, or with median and range.
Study timetable	
 7 years of inclusion

GCP Statement:	This study will be conducted in compliance with the protocol, the current version of the Declaration of Helsinki and applicable guidelines as well as all national legal and regulatory requirements.
-----------------------	---

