4. STUDY OBJECTIVES

The **primary objective** of this retrospective observational single-center study is to describe the efficacy of PGT-M in a real-life setting. Efficacy will be evaluated in terms of live birth rate (LBR), simple and cumulative live birth rate (CLBR) per couple, and abortion rate (AR). Furthermore, investigators will consider how many cycles the participants need to undergo to achieve a viable blastocyst.

The **secondary objective** is to evaluate the incidence of aneuploidy in tested embryos, in order to understand the need for PGTA in addition to PGTM.

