3.1. Endpoints

For the evaluation of the study objectives, all patients that underwent PGTM from 2016 to 2022 will be

included in the study.

The results obtained from the PGT-M will be calculated as:

Live birth rate (LBR): defined as the “the number of deliveries that resulted in at least one live birth, divided by the number of cycles.”

Embryology and Alpha Scientists in Reproductive Medicine. Electronic address [1]

Cumulative live birth (CLBR) per couple: defined as the “delivery of at least one live-born infant (>24 weeks of gestation) in the fresh or in the subsequent frozen-thawed cycles in relation to the number of oocytes retrieved per couple.” Polyzos, Drakopoulos [2]

Abortion rate (AR): is defined as the “spontaneous demise of a pregnancy before the foetus reaches viability. The term therefore includes all pregnancy losses (PLs) from the time of conception until 24 weeks of gestation.” Group, Vlasisavljevic [3]

Aneuploid embryo rate: “the most common genetic abnormality resulting in embryonic demise, pregnancy loss, and congenital birth defects. At the preimplantation stage, ~50% of the IVF-derived embryos have chromosomal abnormalities that are incompatible with implantation or normal fetal development.” Hindi E. Stohl [4]

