7.2. Case Report Forms

Data will be collected and included in a Microsoft Excel sheet. For each patient negative or affirmative answer will be registered for each of the 567 cycles. The investigator at each site will ensure the accuracy, completeness, and timeliness of the data. The data will be collected anonymously, and patients will be identified in the database with successive numbers. Participants will not be identified in the CRF by name or initials and birth date and appropriate coded identification will be used.

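### The figure 567 is given as embryos, children born and cycles in three places, and section 6.1 defines a sample of children that contradicts the all-PGT-M-patients sample set elsewhere

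*Protocol*

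**What the plan says.** **The number 567 appears three times, with a different unit each time.**

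- Section 2 (Study flow-chart), in the row for PGT-M analysis: 567 embryos.
- Section 6.1 (Sample size): "all the children born from single thawed embryos in Fertility Center from the beginning to 2016, will be included in the study", followed by "and the sample is 567".
- Section 7.2 (Case Report Forms): "For each patient negative or affirmative answer will be registered for each of the 567 cycles".

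**The population is stated consistently outside section 6.1.** Section 1 (Summary) gives the planned number as "All 76 patients who underwent PGTM testing in the Fertility Center starting from the beginning of 2016 and going through the end of 2022". Its endpoints entry states that "all patients that underwent PGTM from 2016 to 2022 will be included in the study", and section 3.1 (Endpoints) repeats this. Sections 4.1 (Inclusion criteria) and 4.3 (Recruitment) also take all PGT-M patients, and section 4.2 (Exclusion criteria) excludes nobody. On the data source, the Summary says: "The study database includes all PGTM cycles performed between 2016-2022 at the Humanitas Fertility Center".

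**The outcomes depend on these counts.** The live birth rate (LBR) is "the number of deliveries that resulted in at least one live birth, divided by the number of cycles". The primary objective also covers the cumulative live birth rate (CLBR) per couple and the abortion rate, and adds that "investigators will consider how many cycles the participants need to undergo to achieve a viable blastocyst".

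**The concern.** Embryos tested, treatment cycles and live-born children are successive levels of one process, and one figure cannot be expected to count all three. At least two of the three labels therefore look wrong, and the reader cannot tell which to trust.

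Section 6.1 also describes a different study population. Its unit is the child, it does not mention PGT-M, it restricts births to single thawed embryos, and its time window ends at 2016 where the Summary's starts there.

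Two things are at stake:

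1. A sample made up of live-born children is selected on the outcome. Couples without a birth are absent, so LBR, CLBR, the abortion rate and the number of cycles needed to reach a viable blastocyst cannot be estimated from it. Together these are the whole primary objective.
2. LBR is a per-cycle rate, and the only cycle count printed in the protocol is the 567 of section 7.2. If that figure really counts embryos, using it as the denominator would understate LBR.

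**Working it through.** No sample-size formula applies. The study is descriptive, takes all available records, and states no alpha, power or effect size, so there is no derivation of 567 to reproduce. The check compares the labels and then sizes the consequence.

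**Inputs from the protocol**

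- 76 patients (Summary, planned number).
- 567, as embryos (flow-chart), as children (section 6.1) and as cycles (section 7.2).
- LBR = deliveries with at least one live birth / number of cycles (section 3.1).

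**Input not in the protocol:** the number of PGT-M cycles. I take at least one per patient, that is 76, treating each of the 76 patients as a separately treated woman or couple. Averages of two and three cycles per patient are assumptions for illustration.

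**Step 1: 567 against 76 patients.** 567 / 76 = 7.46 per patient.

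| Unit of 567 | Implied average | Reading |
|---|---|---|
| Embryos analysed | 7.46 embryos per patient; 7.5, 3.7 or 2.5 per cycle at 1, 2 or 3 cycles per patient | Compatible |
| Live-born children of the study patients | 7.46 children per patient in seven years | Not credible |
| Cycles | 7.46 PGT-M cycles per patient in seven years | Doubtful, but not excluded by the protocol |

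Section 6.1 does not limit its children to PGT-M. Read literally, 567 could be a count of births at the centre outside the study population. It would then say nothing about this study's sample, and its equality with the embryo count would be unexplained.

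**Step 2: can two labels hold together?** If 567 were both embryos analysed and children of the study patients, there would be as many children as embryos tested. The protocol itself distinguishes affected from unaffected embryos and plans an abortion rate, so it does not expect that. If 567 were both embryos and cycles, exactly one embryo per cycle would have been analysed on average. Nothing in the protocol says so.

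**Step 3: population, side by side**

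| Feature | Section 6.1 | Rest of the protocol |
|---|---|---|
| Unit | Children born | Patients who underwent PGT-M |
| PGT-M required | Not mentioned | Yes |
| Period | Up to 2016 as worded | 2016 to 2022 (Summary, section 3.1) |
| Transfer type | Single thawed embryos only | No such limit; the CLBR definition counts births from fresh and frozen-thawed cycles |
| Patients without a birth | Left out | Included; no exclusions (section 4.2) |

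The period is probably a slip for the Summary's wording, which starts at the beginning of 2016. Correcting it would leave the other four rows in conflict.

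**Step 4: effect on LBR if 567 counts embryos but is used as the cycle count.** With D deliveries and C true cycles, reported LBR / true LBR = (D / 567) / (D / C) = C / 567.

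| Cycles per patient | C | C / 567 | Reported LBR too low by a factor of |
|---|---|---|---|
| 1 (minimum) | 76 | 0.134 | 7.46 |
| 2 (assumed) | 152 | 0.268 | 3.73 |
| 3 (assumed) | 228 | 0.402 | 2.49 |

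If 567 really is the number of cycles, this error does not arise and the flow-chart's unit or number is in doubt instead.

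**The case against.** The best defence is that neither harm need occur. Who enters the study is governed by the inclusion, exclusion and recruitment sections, which are clear and agree with the Summary; a single sentence in section 6.1 departs from them. The LBR denominator is defined as the number of cycles, and the registry holds all PGT-M cycles for 2016 to 2022. In a retrospective study the rate is computed from the records, and no section says that 567 will be the denominator. The study has no power calculation, so no design decision rests on the figure. Sections 4.3 and 10 foresee collecting data on children, which gives the mention of children in section 6.1 some context.

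Three narrower points are also fair. The floor of 76 cycles treats each patient as a separately treated woman or couple, although the protocol uses both patients and couples without linking them. Calling 7.46 cycles per patient doubtful is a judgement, because the protocol gives no figure for cycles per patient. And nothing is miscalculated: this is an inconsistency of units and population.

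Much of this stands. The harm is conditional, and the 13% to 40% range is not an expected bias. But the objection does not remove the contradiction. The eligibility sections do not say what 567 counts, and the foreseen child data do not make 567 a count of children. Section 6.1 remains the sample statement in the statistical section, and as written it names a sample from which the primary outcomes cannot be estimated.

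**Conclusion.** The concern holds, with high confidence, and should be corrected. The protocol gives 567 three incompatible units, and section 6.1 states a population that conflicts with the Summary, section 3.1 and sections 4.1 to 4.3. The embryo label fits best beside 76 patients, but the document does not settle the matter.

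The consequence is conditional. If section 6.1 were followed, the sample would be selected on live birth and the primary objective could not be met. If 567 counts embryos and were used as the cycle count, the reported LBR would be 13% of the true value at one cycle per patient, 27% at two and 40% at three. The first figure assumes one treated woman or couple per patient; the other two rest on assumed cycle averages. If section 6.1 is ignored and cycles are counted from the registry, neither error occurs, but the protocol text is still wrong.

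**What to change.** 1. Check in the registry what 567 counts, and obtain two totals for 2016 to 2022: PGT-M cycles performed and embryos analysed by PGT-M.
2. Replace section 6.1 with a statement along these lines: *The sample is every patient treated with PGT-M at the centre between the start of 2016 and the end of 2022, whatever the outcome (76 patients), with [n] PGT-M cycles and [n] embryos analysed by PGT-M.* Remove the references to children born and single thawed embryos, and the window ending at 2016.
3. Correct the unit or the number in section 7.2, the flow-chart or both, to match the registry.
4. Use the registry count of PGT-M cycles as the LBR denominator, not an unverified 567.

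The cost is a wording amendment and two registry counts. No new patients, procedures or data collection are needed.

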6.2. Analysis

Data will be described as number and percentage, if categorical, or mean and standard deviation, if continuous and approximately Gaussian, or with median and range, otherwise. Adherence to Gaussian distribution will be checked with Shapiro Wilks test.

7. QUALITY ASSURANCE AND CONTROL

7.1. Data handling and record keeping /archiving

The investigator must keep the documents on file for at least 7 years after completion or discontinuation of the study. After that period, the documents may be destroyed, subject to local regulations. Before proceeding to documents' destruction, sites must inform the Coordinating Investigator/delegate in writing.

Should the investigator wish to assign the study records to another party or move them to another location, the Coordinating Investigator/delegate must be notified in advance.

7.2. Case Report Forms

Data will be collected and included in a Microsoft Excel sheet. For each patient negative or affirmative answer will be registered for each of the 567 cycles. The investigator at each site will ensure the accuracy, completeness, and timeliness of the data. The data will be collected anonymously, and patients will be identified in the database with successive numbers. Participants will not be identified in the CRF by name or initials and birth date and appropriate coded identification will be used.

7.3. Source documents

Source data must be available at the site to document the existence of the study participants. Source data include the original documents relating to the study, as well as the medical treatment and medical history of the participant.

8. CONFIDENTIALITY OF PATIENT RECORDS

The investigator assures that patients' anonymity should be maintained and that their identities are protected from unauthorized parties. Particular attention should be paid whenever patient data are supplied to third parties and may be autonomously processed.

The investigator should keep in a confidential way a patient identification log recording both patient code and name. The investigator should also maintain patients' written consent forms, in strict confidence (i.e., not for submission to the Coordinating Investigator).

Any investigator and/or research staff member who has a conflict of interest with this study (such as patent ownership, royalties, or financial gain greater than the minimum allowable by their institution) must fully disclose the nature of the conflict of interest.

9. ETHICAL CONSIDERATIONS

The responsible investigator ensures that this study is conducted in agreement with this protocol, the Good Clinical Practice, the current version of Declaration of Helsinki and the applicable regulations.

The protocol and any amendments are subject to review and approval by the competent Independent Ethics Committee(s) (“IEC”).

10. INFORMED CONSENT

Documented informed consent to access patients’ information after fertility treatment for research purposes has been obtained before fertility treatment. Informed consent signed by the patient allows the staff of Fertility Center to recontact telephonically patients to collect further information about pregnancy evolution and follow up. The written informed consent form has been signed and personally dated by the patient or by the patient’s legally acceptable representative, and by a medical doctor employed in the Fertility Center.

Moreover, during recruitment, all patients will be informed of the aims of the study. Verbal consent will be collected to gather information about the children considered; the patient is free to deny consent to answer all or any question. Participation is voluntary and does not prejudice the patient’s subsequent care.

Patients will be informed as to the strict confidentiality of collected data.

11. DATA OWNERSHIP

Istituto Clinico Humanitas is the owner of the data resulting from the study. All centers and investigators participating in the study should be made aware of such circumstances and not disseminate information or data without the prior written consent by Istituto Clinico Humanitas.

12. PUBLICATION POLICY

After completion of the study, the Coordinating Investigator prepares a draft manuscript containing results of the study based on the statistical analysis. The manuscript is delivered to the co-authors for comments and then sent to a scientific journal for publication.

All publications, abstracts, presentations, manuscripts, and slides - issued by the Investigators of the collaborative sites and including data from the present study- should be submitted to and reviewed by the Coordinator Investigator at least 3 (three) weeks in advance the planned date for the submission to the scientific journal.

13. FUNDING AND SUPPORT

NA

